#### **5.5. Prior and Concomitant Medications**

Prior medications are defined as those taken before the date of the study drug. Concomitant medications are defined as any non-study medication taken during the study i.e. on or after the date of the study drug and within 90 days of the study drug treatment.

The number and percentage of subjects taking prior and concomitant medications will be tabulated separately by anatomical-therapeutic-chemical (ATC) level 2 and preferred drug name by treatment for the safety analysis set. A subject taking the same medication multiple times is counted only once under that preferred drug name. The summary will be sorted in the alphabetic order of ATC classes and preferred terms.

Prior and concomitant medications will be listed with flag.

Medications are coded using the World Health Organization (WHO) Drug dictionary B3 enhanced, version Mar 2020.

#### **5.6. Study Treatments and Extent of Exposure**

Study drug exposure will be summarized descriptively by treatment for the safety analysis set:

- Duration of infusion (minutes)
- Received the full injection volume (Yes or No)
- Infusion interrupted (Yes or No)
  - Reasons for infusion interruption (Adverse event, Technical Issue, Other)
- Infusion resumed (Yes or No)

The study drug administration details including the administration date and time will be presented in a by-subject listing.

#### **5.7. Efficacy Analysis**

All efficacy endpoints will be analyzed for the mITT analysis set. The primary and secondary endpoints will also be performed for the Per-protocol analysis set. Treatment comparisons will be for each KPL301 arm vs placebo.

### **5.7.1. Multiplicity Adjustment**

No multiplicity adjustment will be applied for the Phase 2 part of the study.

### **5.7.2. NIAID Scale and Missing Data Imputation for Binary Endpoints**

When two or more NIAID scores are collected on the same study day, the lowest score will be used, except at the date of discharge, in which the highest NIAID score will be used.

Baseline NIAID scores are derived from Day 1 or screening assessment:

- If screening and day 1 are the same day, and screening assessment is available, then the screening NIAID will be used as baseline.
- If screening and day 1 are not on the same day, or screening NIAID assessment is missing, the score from Day 1 will be used as baseline.

For endpoints where the event of interest is favorable, like proportion of subjects alive and free of ventilation, and proportion of subjects with 1-point/2-point clinical improvement, the following imputation rule of NIAID scale will be adopted:

- When the NIAID assessment is missing at the target day (Day 15, 29, etc.), the NIAID score closest to and within 2 days of the target day will be used. In case of ties with equal number of days on either side of target day, the value before the target day will be used.
- When no NIAID assessment is available within 3 days of the target day, the primary treatment comparison will be based on a combination of responder imputation and non-responder imputation:
  - Discharged subjects will be considered as having had the event (responders).
  - Subjects who are still in the hospital will be considered as not having had the event (non-responders).
  - Subjects who terminate the study early including death will be considered as not having had the event for all subsequent target days after discontinuation (non-responders).

In calculation of the mortality rate, a subject with the last known alive date on or after the target day is considered alive. If the last known alive date is before the target day but within 2 days of the visit window, the subject is considered alive at the target day. Since survival sweep will be conducted for each database lock, minimum missing mortality status is expected.

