#### **5.7.2. NIAID Scale and Missing Data Imputation for Binary Endpoints**

NIAID scores at randomization should be derived from the last NIAID assessment prior to randomization. When not able to be derived, the screening NIAID will be used unless missing, in which case the (first) score from Day 1 will be used.

Baseline NIAID scores should be derived from the last NIAID assessment prior to dosing.

When two or more NIAID scores are collected on the same study day, the lowest score will be used, except at the date of discharge, in which the highest NIAID score will be used. When the derived NIAID at randomization happens to be from Day 1, then the Day 1 NIAID should be the lowest score on or after the NIAID at randomization time.

For endpoints where the event of interest is favorable, like proportion of subjects alive and free of ventilation, and proportion of subjects with 1-point/2-point clinical improvement, the following imputation rule of NIAID scale will be adopted:

- When the NIAID assessment is missing at the target day (Day 15, 29, etc.), the NIAID score closest to and within the window of the target day will be used. In case of ties with equal number of days on either side of target day, the value before the target day will be used. The window is (-2 days, +2 days) for Day 15 endpoints, (-2 days, +4 days) for Day 29 endpoints, and (-7 days, +14 days) for Day 90 endpoints.
- When no NIAID assessment is available within the window of the target day, the primary treatment comparison will be based on a combination of responder imputation and non-responder imputation. The rules taking into consideration of missing data are mostly related to subjects being improved and discharged from the hospital.
  - Discharged subjects will be considered as having had the event (responders).
  - Subjects who are still in the hospital will be considered as not having had the event (non-responders).
  - Subjects who died will be considered as not having had the event for all subsequent target days after discontinuation (non-responders).

- Subjects who terminated study before the target day, if the NIAID met the endpoint criteria as of last assessment before the study termination, they will be considered as having had the event for all subsequent target days after discontinuation (responders).
- Subjects without any post randomization assessment will be considered non-responders.

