### **2.2. Secondary Efficacy Endpoints**

#### **Cohort 1 (Non-ventilated Subjects)**

1. Time to 2-point clinical improvement by Day 29

Defined as time from randomization to a 2-point improvement on the NIAID 8-point ordinal scale, or discharge from the hospital, whichever comes first. Subjects who die before Day 29 will be censored at Day 30.

2. Time to return to room air or discharge by Day 29

Defined as time from randomization to breathing room air (NIAID scale  $\geq 5$ ), or discharge from the hospital, whichever occurs first. Subjects who die before Day 29 will be censored at Day 30.

3. Mortality rate at Day 29

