### **4.2.2. Day 1**

**Day 1** is defined as the day of the study treatment after randomization.

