### **4.2.3. Baseline Values**

Baseline is defined as the last non-missing value obtained prior to the start of study treatment. The baseline NIAID is defined separately in Section [5.7.2](#).

The change from baseline values will be derived for each subject as the post-baseline evaluation minus the baseline evaluation.

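### When Phase 2 baseline NIAID is taken from the dosing day, the SAP does not require a pre-dose score, so a recorded post-dose worsening can lower baseline and bring improvement forward

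*Combined protocol and SAP*

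**What the plan says.** Phase 2 SAP section 4.2.3 sets the general rule: "Baseline is defined as the last non-missing value obtained prior to the start of study treatment". It then removes NIAID from that rule and refers the reader to section 5.7.2.

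Section 5.7.2 has two baseline bullets.
- If screening and Day 1 fall on the same day and a screening score exists, "then the screening NIAID will be used as baseline".
- In the remaining cases the source of baseline changes, where "screening and day 1 are not on the same day, or screening NIAID assessment is missing, the score from Day 1 will be used".

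Section 4.2.2 says that Day 1 "is defined as the day of the study treatment after randomization". Section 5.7.2 also has a same-day rule, "When two or more NIAID scores are collected on the same study day, the lowest score will be used", whose only exception is the date of discharge.

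The first Cohort 1 secondary endpoint in Phase 2 SAP section 2.2 is "Time to 2-point clinical improvement by Day 29", with hospital discharge also counting as the event. Section 4.1 says that a subject randomized under the wrong cohort is analysed in the cohort indicated by baseline NIAID: 3 or 4 for Cohort 1, 2 for Cohort 2.

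The Phase 3 SAP, also in its section 5.7.2, words the rule differently: "Baseline NIAID scores should be derived from the last NIAID assessment prior to dosing".

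**The concern.** A baseline should describe the subject before treatment can act. Here the one variable on which the improvement endpoints rest is exempted from the pre-treatment rule that covers every other variable. Its replacement names a calendar day, and that day includes the hours after the infusion. Low NIAID scores are worse, so keeping the lowest score of the day pulls baseline down whenever a post-dose deterioration is recorded on Day 1. Recovery is then measured from the deteriorated state.

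Two things are at stake. First, improvement in Cohort 1 can be credited before the subject has gained anything over entry status, and baseline can depend on treatment. Second, because baseline NIAID also settles cohort membership for misrandomized subjects, a Cohort 1 subject intubated after dosing on Day 1 would carry a baseline of 2 and could be read as Cohort 2. That would take the subject out of the Cohort 1 primary analysis. The Phase 3 SAP introduction also announces selected outputs that pool the two phases, and these would combine two definitions of baseline.

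**Working it through.** The plan states no figure on this point, so there is nothing to reproduce. The check applies both rules to the same score paths.

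**Rules.** Let *b* be baseline and *K* the required gain. The event falls on the first day with score ≥ *b* + *K*, or at discharge (score 7 or 8).
- Phase 2 text, with screening on an earlier day or its score missing: *b* = the minimum of all Day 1 scores.
- Pre-dose rule, as in the Phase 3 SAP: *b* = the last score before infusion.

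**Direction.** If a pre-dose Day 1 score exists, the minimum over the day cannot exceed it. The threshold *b* + *K* is therefore never higher under the Phase 2 text, and the event is never later. If only a post-dose score exists, baseline can move either way. It is still a post-treatment value.

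**Constructed paths, *K* = 2.** These are hypothetical and only show the mechanism.

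| Pre-dose | Post-dose Day 1 | Scores from Day 2 | Phase 2 text: baseline, threshold, day | Pre-dose rule: baseline, threshold, day | Days early |
|---|---|---|---|---|---|
| 4 | 3 | 3,3,4,4,5,5,6,6,7 | 3, 5, Day 6 | 4, 6, Day 8 | 2 |
| 3 | 2 | 2,2,2,3,3,4,4,5,5,7 | 2, 4, Day 7 | 3, 5, Day 9 | 2 |
| 4 | 2 | 2,2,3,3,4,4,4,5,6,7 | 2, 4, Day 6 | 4, 6, Day 10 | 4 |
| 4 | none | 4,4,5,5,6,7 | 4, 6, Day 6 | 4, 6, Day 6 | 0 |

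In the third path the event is counted on Day 6 at a score of 4, the score at which the subject entered. In the second and third paths the Phase 2 baseline is 2, which is the Cohort 2 value.

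**Which endpoints are reached.**
- Of the three Phase 2 Cohort 1 secondaries, only the first uses change from baseline. Return to room air has a fixed threshold (score of 5 or more), and the third is mortality.
- The K-point improvement rates in sections 5.7.2 and 5.7.3 use baseline.
- Cohort 2 subjects enter at 2, and the only lower score is death. The lowering mechanism has essentially no room to act on their 1-point endpoint.
- The response criteria of both primaries (alive without mechanical ventilation at Day 29; death by Day 29) do not refer to baseline. Only the cohort-assignment route could touch them.

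**The case against.** Several arguments narrow the point.

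**Collection practice.** The protocol's summary of changes shows that Amendment 2, on which the Phase 2 SAP rests, replaced highest and lowest daily values by a single morning assessment. With one score there is no lowest to choose. This reduces the exposure but does not remove it. The Phase 2 SAP introduction says that some data collection may reflect Amendment 1, and a morning score is not tied to the time of infusion.

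**Footnote 11.** The current Schedule of Activities says that Day 1 assessments should precede dosing. The change-log extracts do not show that sentence in force before Version 5. It is also guidance to sites, not a condition in the SAP, and does not stop a second Day 1 score from being selected.

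**Protocol section 10.1.1.** Each NIAID entry records the worst status of the previous day. On one reading, a Day 1 entry describes the day before dosing. The wording is ambiguous and does not settle the matter.

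**Specific over general.** The first baseline bullet prefers the screening score, and the second speaks of one score, "the score from Day 1 will be used as baseline". The authors may have meant the entry score, outside the lowest-of-day rule. That is plausible, but the text does not say it. The Phase 3 SAP foresees several Day 1 scores and separates baseline from the lowest of the day.

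**Limited reach.** Phase 2 uses a two-sided alpha of 0.20 without multiplicity adjustment, and time to 2-point improvement is not a current Cohort 1 secondary. Phase 3 already uses a pre-dose baseline. All of this stands and bounds the importance of the point.

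**Timing.** Phase 2 results have been reviewed and used to revise Phase 3, so replacing the definition now would alter a pre-specified variable after unblinding. This stands, and it determines the form of the fix.

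**Conclusion.** The point holds as a conditional defect in the Phase 2 derivation rule. It needs three things together: screening on a day other than Day 1 or a missing screening score; a post-dose score recorded under Day 1; and that score being worse than the pre-dose score. When all three are met, baseline is a post-treatment value and Cohort 1 improvement can be credited early, by 2 to 4 days in the constructed paths. Subjects screened and dosed on the same day with a screening score available are unaffected.

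A reader might go further in three ways, none supported by the documents.
- **That Phase 2 improvement results favour mavrilimumab.** The rule is the same in all arms and helps whichever arm has more recorded Day 1 worsening. No direction can be fixed.
- **That a stated share of the cohort was credited early.** Any percentage would need daily transition rates, the frequency of earlier-day screening and the frequency of second Day 1 scores. The documents give none of these.
- **That the primary endpoints or Phase 3 are compromised.** The primary response criteria do not use baseline, and Phase 3 defines it before dosing. Two narrower routes remain: cohort assignment by baseline NIAID in Phase 2, and any pooled output that carries the Phase 2 definition forward.

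**What to change.** Define Phase 2 baseline NIAID as the last assessment before the start of infusion, as in Phase 3 SAP section 5.7.2, and use the screening score if there is no pre-dose Day 1 score. State that the lowest-of-day rule applies only to post-dose scores, and leave the discharge-date exception as it is.

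Because Phase 2 is already unblinded, keep the pre-specified results and add the re-derived improvement endpoints as a labelled post hoc sensitivity analysis. Accompany it with a listing, by arm, of subjects whose baseline or analysis cohort changes. If the listing is empty, that closes the question. Use the pre-dose definition in every pooled Phase 2/3 output.

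The cost is a short SAP addendum and the re-derivation of one variable from existing data. This assumes that Day 1 scores can be ordered relative to the infusion; scores that cannot be ordered should be flagged in the listing.

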### **5.7.3. Censoring Rules for Time to Event Endpoints**

Since scheduled visits allow windows (2-day for Day 15 and Day 29, and 7-day for Day 60 and 90), NIAID scores collected within visit windows of the target days will be used for time to event analysis by the corresponding target day. The last assessments referred to in this section include those occur after the target day but within the protocol-defined visit window, in which cases the date of the target day instead of the actual day will be used for calculation of time. For example, if a subject has not had 2-point clinical improvement by Day 29 visit, which occurs on Day 30, the subject will be censored at Day 29 instead of Day 30 or Day 22 (the assessment before Day 29).

- Time to ventilation or death by Day 29  
Defined as time (in days) from randomization to the date of death or start date of using mechanical ventilation (NIAID  $\leq$  2) by Day 29 for Cohort 1. All subjects who have never had

NIAID  $\leq 2$  by Day 29 will be censored at the last assessment date of NIAID 8-point ordinal scale.

- [REDACTED]
- Overall survival by Day X (X=29, or 90)  
Defined as time (in days) from the randomization date to the date of death by Day X. All survival subjects will be censored at last date known alive on/before Day X.
- [REDACTED]
- Time to K-point clinical improvement by Day X (K=1, or 2, X=15, or 29)  
Defined as time (in days) from randomization to the date of a K-point improvement on the NIAID 8-point ordinal scale, or discharge from the hospital, whichever occurs first, by Day X. Alive subjects who do not have K-point improvement nor discharge from the hospital will be censored at the date of the last NIAID 8-point ordinal scale assessment on/before Day X. Dead subjects will be censored at Day X +1.
- [REDACTED]
- [REDACTED]

#### 5.7.4. Analysis of Primary Efficacy Endpoint

The proportion of subjects alive and free of ventilation at Day 29 for Cohort 1, and the proportion of subjects who die (mortality rate) by Day 29 for Cohort 2 will be analyzed by Fisher's exact test. The 80% confidence interval (CI) will be calculated using the Clopper-Pearson exact method. Number of subjects and percentages will be summarized by treatment. The 80% CI of the difference in the proportion (KPL-301 – placebo) based on normal approximation will be provided.

Cochran-Mantel-Haenszel (CMH) test adjusting for the randomization strata (standard of care antiretroviral therapy, age, and ARDS status) will be used as supportive analysis of the primary efficacy endpoint for Cohort 1. The CMH method addresses the global null hypothesis of no difference between treatments in all of the strata. Hence, it corresponds to, in all strata, the risk difference being 0, the risk ratio being 1, and the odds ratio being 1. The CMH p-value is the same

across odds ratio/risk ratio/risk difference. In addition to CMH p-value, the stratified risk difference and the stratified odds ratio will be provided in our analyses.

Analysis of the primary efficacy endpoint based on the per protocol population will be conducted following the same methods.

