## History of Changes

Version Number	Version Date	Notes
1.0	November 9, 2021	Final, submitted to the FDA.
2.0	December 13, 2021	
Amendment, to be submitted to the FDA.
 
The following changes are made per FDA feedback on SAP V1.0:
 

1) As per FDA guidance, the ITT definition was reverted back to the original definition to clarify unequivocally that all randomized subjects will be in the ITT analysis set.

2) For binary endpoints, specified the CMH test stratified by randomization strata as the main method for the 95% CI. Removed the 95% CI based on normal approximation.

3) Added sensitivity analysis using multiple imputation methods to handle missing data in binary endpoints.

4) Added details for tipping point analysis and reference.

 
The definition of NIAID at randomization and Day 1 NIAID are further clarified via some editorial changes.

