### 1.4. Sample Size Justification

Sample sizes were calculated separately for each cohort and phase of the study based on their primary endpoint and other assumptions. Key elements for Phase 2 sample size are summarized below with type I error of 0.20 and power of 80%.

Cohort	KPL-301	Placebo	Sample Size	Primary Endpoint
1	95%	75%	120	D29 Proportion of subjects alive and free of ventilation
2	40%	80%	51	D29 Mortality rate

Approximately 171 subjects will be randomized to the Phase 2 part of this study.

Sample size estimation for Cohort 1 (non-ventilated subjects) in Phase 2 is based on the primary efficacy endpoint proportion of subjects alive and free of mechanical ventilation at Day 29, using a Fisher’s exact test.

Approximately 120 subjects will be randomized with a 1:1:1 allocation ratio. Assuming the proportions of subjects alive and free of ventilation at Day 29 are 95% and 75% for the active treatment arm and placebo arm, respectively, 40 subjects per arm will achieve a minimum 80% power for a pairwise comparison versus control when the two-sided alpha value is 0.20.

Sample size for Cohort 2 (ventilated subjects) in Phase 2 is based on the primary efficacy endpoint mortality rate at Day 29, using a Fisher's exact test. Approximately 51 subjects will be randomized with a 1:1:1 allocation ratio. Assuming the mortality rates at Day 29 are 40% and 80% for the active treatment arm and placebo arm, respectively, 17 subjects per arm will achieve 80% power for a pairwise comparison versus control when the two-sided alpha value is 0.20.

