### **4. GENERAL STATISTICAL CONSIDERATIONS**

Analyses described in this SAP will be conducted separately for each of the two cohorts.

Summary statistics for continuous variables will include n (non-missing observations), mean, standard deviation, minimum, median, and maximum. Summary statistics for categorical variables will be presented in terms of frequencies and percentages based on the analysis set unless otherwise specified. In by-visit summary tables, only scheduled visits/timepoints will be summarized.

Time to event data will be summarized using the Kaplan-Meier (KM) method, which will include the estimated median, 25th percentiles, 75th percentiles, and their 80% confidence interval (CI). The CIs will be calculated using a log-log transformation. The event-free probability and its 80% CI will be calculated at days 4, 8, 15, 22, 29, 60 and 90 as appropriate using Greenwood's formula with a log-log transformation.

The 80% confidence interval (CI) of the difference in the proportion (KPL-301 – placebo) will be primary based on normal approximation when comparing treatment for binary (proportion or rate) endpoints.

All relevant subject data will be listed by cohort, treatment, subject and visit/time point including both scheduled and unscheduled visits.

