#### **5.7.5.2. Binary (rate or proportion) endpoints**

The primary treatment comparison for all binary endpoints will be based on the Fisher's exact test. Number of subjects and percentages will be summarized by treatment. The 80% confidence interval (CI) of the difference in the proportion (KPL-301 – placebo) based on normal approximation will be provided.

The event rates (or event-free) from the corresponding time to event analysis can serve as supportive analyses. For example, proportion of subjects with K-point clinical improvement can be estimated from time to K-point clinical improvement; mortality rate can be estimated from the overall survival. No formal testing will be conducted.

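### In Phase 2 Cohort 2 the normal-approximation 80% interval for a difference in proportions under-covers modestly, by about 2 to 3 points on average near the design rates

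*Combined protocol and SAP*

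**What the plan says.** The Phase 2 SAP gives one method for the interval around a treatment difference in proportions.

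- Section 4 sets the general rule: the 80% interval "will be primary based on normal approximation when comparing treatment for binary (proportion or rate) endpoints".
- Section 5.7.4 repeats it for the primary endpoint of both cohorts: "The 80% CI of the difference in the proportion (KPL-301 – placebo) based on normal approximation will be provided".
- Section 5.7.5.2 repeats it for the remaining binary endpoints: "The 80% confidence interval (CI) of the difference in the proportion (KPL-301 – placebo) based on normal approximation will be provided".

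No continuity correction is mentioned. The Cohort 1 supportive CMH analysis adds a stratified risk difference but specifies no interval for it.

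The other choices in Section 5.7.4 are exact. The primary endpoints "will be analyzed by Fisher's exact test", and "The 80% confidence interval (CI) will be calculated using the Clopper-Pearson exact method", which I read as the interval for each arm's own proportion.

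Section 1.4 plans 17 subjects per arm in Cohort 2: "Assuming the mortality rates at Day 29 are 40% and 80% for the active treatment arm and placebo arm, respectively". It plans 40 per arm in Cohort 1, at 95% and 75%. Protocol Section 13.3.1 adds a 15% dropout allowance for Cohort 1.

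**The concern.** A normal-approximation interval centres on the observed difference and estimates its variance from the observed proportions. With 17 per arm, or with proportions near 0 or 1, both steps are rough and actual coverage can fall below nominal. The SAP uses exact methods for the test and the per-arm intervals, then a large-sample formula for the one interval that compares arms.

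What is at stake is the reported precision of the Phase 2 effect estimates. An 80% interval that covers 76% to 78% of the time claims somewhat more certainty than it has. It can also exclude zero where Fisher's test does not reject.

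**Working it through.** **Inputs.** From Phase 2 SAP Section 1.4: Cohort 2, 17 per arm, 40% and 80%; Cohort 1, 40 per arm, 95% and 75%; two-sided alpha 0.20. From protocol Section 13.3.1: 15% dropout in Cohort 1, so 40 × 0.85 = 34 evaluable per arm. From protocol Section 13.3.2: the revised Cohort 1 rates, 87.5% and 74.4%.

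**Step 1: the plan's own figure.** Fisher power is the sum, over all pairs (x1, x2), of b(x1; n, p1) × b(x2; n, p2) for tables with p ≤ 0.20, where b is the binomial probability.

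- Cohort 2: 81.35% at 17 per arm and 77.9% at 16, so 17 is the smallest size reaching the stated 80%.
- Cohort 1: 80.6% at 34 per arm and 85.7% at 40.

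The stated power reproduces.

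**Step 2: coverage.** The documents state no coverage figure. Write d = x1/n − x2/n for the observed difference and δ = p1 − p2 for the true one. Coverage is the same double sum over tables where

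|d − δ| ≤ 1.2816 × √[p̂1(1 − p̂1)/n + p̂2(1 − p̂2)/n].

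Below, Wald means this interval without continuity correction.

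| Setting | Wald | Newcombe |
|---|---|---|
| Cohort 2, 17/arm, 40% vs 80% | 74.5% | 81.7% |
| Cohort 2, 17/arm, 80% vs 80% | 75.8% | 81.0% |
| Cohort 2, 17/arm, mean over active 30–50%, placebo 70–90% | about 77.6% | about 79.3% |
| Cohort 1, 40/arm, 87.5% vs 74.4% | 77.9% | 80.2% |

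Other Wald results for Cohort 1 are 80.3% (40 per arm) and 79.5% (34 per arm) at 95% vs 75%, and 78.3% (40 per arm) at 75% vs 75%. Miettinen-Nurminen gives 80.0% at the Cohort 2 design point. A simulation of 2,000,000 trials also gives 74.5% for Wald there, and using n − 1 in the variances leaves it at 74.5%.

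**Step 3: how much of 74.5% is discreteness.** At 40% vs 80%, Wald covers 76.1%, 79.3%, 74.5%, 80.1% and 76.5% at 15, 16, 17, 18 and 19 per arm. Around the design rates at 17 per arm it ranges from 72.3% to 81.0%. The mean of 77.6% is a shortfall of 80 − 77.6 = 2.4 points. With 80% mortality in both arms the shortfall is steadier: 75.7% to 76.0% at 16 to 18 per arm.

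**Step 4: why it misses.** At the Cohort 2 design point the true difference lies above the interval in 15.0% of trials and below it in 10.5%, against 10% each nominally. The difference is active minus placebo mortality, so most of the excess misses overstate benefit. Length is not the cause, since mean width is 0.380 for Wald and 0.370 for Newcombe. For example, with 7/17 and 14/17 deaths:

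- d = 0.412 − 0.824 = −0.412
- standard error = √(0.412 × 0.588/17 + 0.824 × 0.176/17) = 0.151
- Wald is −0.605 to −0.218 (width 0.387); Newcombe is −0.576 to −0.200 (width 0.376), placed closer to zero.

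**Step 5: agreement with the test.** At 17 per arm and 80% vs 80%, the Wald interval excludes zero in 100 − 75.8 = 24.2% of trials. Fisher's test rejects in 8.7%, and the two disagree in 15.5%.

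**The case against.** The strongest reply is that this interval is descriptive. Fisher's exact test supplies the p-value for the primary and other binary endpoints, so no Phase 2 test result depends on the interval. That stands. Fisher is conservative, so a score interval would also disagree with it at times.

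The second reply is that 74.5% is a feature of one sample size and one pair of rates, and that score intervals dip too. Newcombe covers 76.6% at 16 per arm with 40% vs 80%, where Wald covers 79.3%. At the Cohort 1 design rates Miettinen-Nurminen covers 78.6% (40 per arm) and 77.9% (34 per arm), slightly below Wald. Enrolment is approximate, so exactly 17 in each arm is not assured. This also stands, and it is why the neighbourhood mean is the fairer summary. It does not remove the point: on a 5-point grid over the same Cohort 2 rates, 84% of settings fall below 80% for Wald, with a mean of 77.0% against 80.1% for Newcombe.

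A reader might infer that the interval influenced the closing of Phase 3 Cohort 2 or the re-planning of Cohort 1. The documents do not support that. Protocol Sections 6.1 and 13.3.2 attribute the closure to the Day 29 primary and secondary results showing no evidence of benefit, and cite no interval. Overstated precision would make a false signal of benefit easier, not harder. The Cohort 1 sample size uses assumed rates, not interval limits.

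A reader might also take the Phase 3 SAP's history entry, "Removed the 95% CI based on normal approximation", as an admission of the same defect. That entry records FDA feedback and a move to a CMH-based interval stratified by the randomization strata. It gives no small-sample reason and concerns Phase 3 only.

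**Conclusion.** The point holds as a modest reporting defect, mainly in Cohort 2. The nominal 80% interval for a difference covers about 77.6% on average near the design rates and about 76% when both arms have 80% mortality. The 74.5% at exactly 17 per arm and 40% vs 80% is correct but should not be quoted as typical.

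Three broader readings are not supported:

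- **Under-coverage throughout Phase 2.** Cohort 1 is nominal at its design rates and about 2 points low at 87.5% vs 74.4% or 75% vs 75%. At a 95% response rate an arm of 40 has no failures with probability 0.95^40 = 12.9%, and so contributes zero variance, yet coverage there is still 80.3%.
- **Intervals that are simply too narrow.** At the Cohort 2 design point the Wald interval is slightly wider than Newcombe, and the problem is location and discreteness.
- **A defective Phase 2 95% interval.** Protocol Section 13.2.4.1 asks for 95% intervals without naming a method, and the Phase 2 SAP ties normal approximation only to the 80% interval.

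The result assumes no continuity correction, which is the natural reading of the text. With one, the interval would over-cover (87.4% at the Cohort 2 design point). It also assumes the planned arm sizes and that every subject contributes an outcome, apart from the 34-per-arm check.

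**What to change.** In Phase 2 SAP Sections 4, 5.7.4 and 5.7.5.2, name a score-type interval for the difference in proportions, either Miettinen-Nurminen or Newcombe, and use the same one throughout. Provide it for the Phase 2 binary endpoints in both cohorts. If Phase 2 is already reported, add it as a supplementary table labelled post hoc, beside the planned intervals. The Fisher p-values stay as they are.

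The cost is SAP wording and a small programming change. Mean widths stay almost the same: 0.380 against 0.370 at the Cohort 2 design rates, and 0.218 against 0.220 at 40 per arm with 87.5% vs 74.4% (planned method first, Newcombe second).
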